8.7.2 Sensitivity Efficacy Analysis

8.7.2.1 Sensitivity Analyses for Absolute Change in Lesion Count

8.7.2.1.1 Repeated Measures

The first sensitivity analyses for absolute change in lesion count (both inflammatory and non-inflammatory) will use a repeated measures ANCOVA, with treatment, analysis center, visit (i.e., Week 2, Week 4 and Week 8), and treatment group by visit interaction as independent factors and a covariate of Baseline lesion count. In this analysis, data from all post-baseline visits will be included with no imputation for missing data.

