2. PREFACE

This Statistical Analysis Plan (SAP) describes the statistical analyses as it is foreseen before breaking the blind. The SAP will serve as a compliment to the study protocol and supersedes it in case of differences. In case of major differences between the study protocol and SAP, e.g. changes in the analysis related to the primary endpoint, a protocol amendment will be considered. The SAP may be updated during the study conduct and will be finalized before breaking the blind.

The following documents were reviewed in preparation of this SAP:

- Clinical Study Protocol SGT-65-04
 - Version 1.0 issued on 23MAR2018,
 - Version 2.0 issued on 01NOV2018,
- Case report form (CRF) for SGT-65-04.
- ICH E9 Guidance on Statistical Principles for Clinical Trials.
- ICH E3 Structure and Content of Clinical Study Reports (CSRs)

The reader of this SAP is encouraged to also read the clinical protocol for details on the conduct of this study, and the operational aspects of clinical assessments and timing for completing a patient in this study.

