8. STATISTICAL AND ANALYTICAL PLANS

8.1 General Methodology

All statistical processing will be performed using SAS® version 9.3 or later unless otherwise stated. Statistical significance will be based on two-tailed tests of the null hypothesis resulting in p-values of 0.05 or less.

The primary method of handling missing efficacy data will be based on estimation using the method of Markov Chain Monte Carlo (MCMC) imputation. The estimation will be done for each treatment group separately so that the pattern of missingness for one group does not influence the estimation of missing data for another group. Groups of complete datasets following the estimation will be concatenated to form analysis datasets for the comparative

analyses and subsequent imputation result inference with SAS PROC MIANALYZE. Descriptive statistics will also be derived from the multiply imputed datasets.

Sensitivity analyses for the primary efficacy endpoints will use 3 methods. For the lesion count endpoint, the first method will use a repeated measures analysis of covariance (ANCOVA), with treatment, analysis center, visit (i.e., Week 2, Week 4 and Week 8), and treatment group by visit interaction as independent factors and a covariate of Baseline. In this analysis, data from all post-baseline visits will be included with no imputation for missing data.

The second sensitivity analyses will use the model based multiple imputation method to impute missing data for the absolute change at Week 12.

The third sensitivity analysis will involve a tipping point analysis.

Similar methods for the dichotomized IGA will involve a repeated measures logistic regression model and a model based multiple imputation and tipping point analysis.

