10. CHANGES IN THE PLANNED ANALYSES

There are no changes in the conduct of the study, but there are minor changes to the planned analyses.

Absolute change from Baseline in inflammatory and non-inflammatory lesion counts from Baseline to weeks 4 and 8 were removed from the supportive efficacy endpoints, as they were also included in the secondary efficacy endpoints.

The pooling analysis described in the protocol is updated in the statistical analysis plan (SAP) to reflect the intended analysis. The protocol discusses pooling sites with five or fewer subjects enrolled in each treatment arm. Taking into consideration the randomization ratio, the SAP requires ten subjects in the active treatment arm and five subjects in the vehicle group.

As part of the pooling analysis, the treatment effect within investigational site must be investigated. The protocol states the site main effect will be examined by using a one-way analysis of variance (for lesion count variables) or a logistic regression analysis (for dichotomized IGA) with a factor of site. The SAP instead explains site will be incorporated into the primary analysis models. Change from Baseline in lesion counts will be analyzed with an ANCOVA (unranked or ranked) with factors of treatment group, investigational site and treatment group by investigational site interaction, and the respective Baseline lesion count variable as a covariate. The dichotomized primary endpoint will be analyzed with a logistic regression with factors of treatment group, investigational site and the interaction term of treatment group by investigational site.

The protocol describes repeated measures sensitivity analyses for the primary efficacy endpoints. Treatment group, analysis center and visit are listed as factors for the repeated measures analyses. In addition to these factors, the SAP includes a factor of treatment group by visit interaction.

The protocol describes imputing only Week 12 data with MCMC imputation, but all missing post-Baseline data will be imputed. The protocol provided did not provide seeds for the IGA MCMC imputation or for the model based multiple imputation, so those were added in the SAP.

Geographic region was removed from the examination of subgroups as all sites in the study are in the United States.

An additional age grouping of 9-11 years, 12-17 years, 18-30 years, and 31 years and older was added to the subgroup summaries.

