Note: Multiple imputation (MCMC) used to impute missing values. Summary statistics represent average values, obtained from averaging the summary statistics generated from each imputed dataset. Negative absolute change values represent decrease from Baseline.

SOURCE: USERNAME\SPONSOR\PROJECT\JOBNAME (DATE, TIME)

Table 14.2.6.1: Sensitivity Analysis of Primary Endpoints: Absolute Change from Baseline in Lesion Counts and Dichotomized IGA Success at Week 12
(Intent-to-Treat Population)
(Page 1 of 2)

	E-BPO/E-ATRA 3%/0.1% Cream (N=xxx)	Vehicle Cream (N=xxx)	Skewness P-Value	Treatment P-Value
Inflammatory Lesion Count – Absolute Change from Baseline				
LSMean ^a	xx.x	xx.x	x.xxx ^b	x.xxx ^a
LSSD ^a	xx.xx	xx.xx		x.xxx ^c
Non-Inflammatory Lesion Count – Absolute Change from Baseline				
LSMean ^a	xx.x	xx.x	x.xxx ^b	x.xxx ^a
LSSD ^a	xx.xx	xx.xx		x.xxx ^c
At Least Two Grade Reduction from Baseline and Achieving Clear or Almost Clear				
Success	xx.x%	xx.x%	N/A	x.xxx ^d
Failure	xx.x%	xx.x%		

^a Least squares means, standard deviations and treatment p-value from a repeated measures analysis of covariance with factors of treatment group, analysis center, visit and treatment group by visit interaction, and the respective Baseline lesion count as a covariate. Negative least squares means values represent decrease from Baseline.

^b Skewness test based on methods presented by J.H. Zar (1984).

^c P-value from a ranked repeated measures analysis of covariance with factors of treatment group, analysis center, visit and treatment group by visit interaction, and the respective Baseline lesion count as a covariate.

^d P-value from a repeated measures logistic regression with factors of treatment group, analysis center, visit and treatment group by visit interaction.

SOURCE: USERNAME\SPONSOR\PROJECT\JOBNAME (DATE, TIME)

Table 14.2.6.1: Sensitivity Analysis of Primary Endpoints: Absolute Change from Baseline in Lesion Counts and Dichotomized IGA Success at Week 12
(Intent-to-Treat Population)
(Page 2 of 2)

	E-BPO/E-ATRA 3%/0.1% Cream (N=xxx)	Vehicle Cream (N=xxx)	Skewness P-Value	Treatment P-Value
Inflammatory Lesion Count – Absolute Change from Baseline				
LSMean ^a	xx.x	xx.x	x.xxx ^b	x.xxx ^a
LSSD ^a	xx.xx	xx.xx		x.xxx ^c
Non-Inflammatory Lesion Count – Absolute Change from Baseline				
LSMean ^a	xx.x	xx.x	x.xxx ^b	x.xxx ^a
LSSD ^a	xx.xx	xx.xx		x.xxx ^c
At Least Two Grade Reduction from Baseline and Achieving Clear or Almost Clear				

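### The repeated-measures sensitivity analyses list visits as Weeks 2, 4 and 8 and name no Week 12 contrast, so they do not ensure a test of the Week 12 co-primary effects

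*SAP*

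**What the plan says.** Both co-primary endpoints (SAP 7.1.1) are at Week 12: IGA success, and absolute change in inflammatory and in non-inflammatory lesion counts.

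For lesion counts, SAP 8.7.2.1.1 specifies a repeated-measures ANCOVA with treatment, analysis center, "visit (i.e., Week 2, Week 4 and Week 8), and treatment group by visit interaction as independent factors", and baseline count as covariate. It then says that "data from all post-baseline visits will be included with no imputation for missing data". SAP 8.1 gives the same list: "visit (i.e., Week 2, Week 4 and Week 8), and treatment group by visit interaction as independent factors and a covariate of Baseline". SAP 8.7.2.2.1 repeats it for the IGA model, which is fitted by generalized estimating equations. The protocol has the same three visits, without the interaction, in the synopsis and in 17.1, 17.4.7.1 and 17.4.7.2.

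The results go into Table 14.2.6.1, titled "Sensitivity Analysis of Primary Endpoints: Absolute Change from Baseline in Lesion Counts and Dichotomized IGA Success at Week 12". Its first page has one least-squares mean per arm for each lesion type and one success rate per arm for IGA. Footnote a describes the lesion-count result as a "treatment p-value from a repeated measures analysis of covariance with factors of treatment group, analysis center, visit and treatment group by visit interaction". Footnote c describes the ranked version in the same terms. Footnote d reads "P-value from a repeated measures logistic regression with factors of treatment group, analysis center, visit and treatment group by visit interaction".

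SAP section 10 records one change to this model: "In addition to these factors, the SAP includes a factor of treatment group by visit interaction".

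**The concern.** There are two separate gaps.

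- **Which visits are in the model.** The list is introduced by i.e., so it defines the factor and does not merely give examples. Taken literally, it drops the time point of the endpoint whose robustness is being tested.
- **Which effect is reported.** Suppose a programmer adds Week 12 from context. In a model with a treatment-by-visit term, a treatment p-value may still be a test averaged over visits. Under reference coding in the IGA model, it may be the effect at whichever visit is the reference.

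Of the three sensitivity methods, this is the only one that uses observed data without imputation. Its value lies in showing whether the Week 12 conclusion depends on how missing data were handled. If it reports a visit average, a result that differs from the primary one may reflect smaller early effects and say nothing about missing Week 12 data. The error can also run the other way: an early effect that has gone by Week 12 could look like confirmation.

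**Working it through.** **1. The text, side by side.**

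| Place | Visits implied | Effect named |
|---|---|---|
| SAP 8.1, 8.7.2.1.1, 8.7.2.2.1, factor list | 2, 4, 8 | none |
| SAP 8.7.2.1.1 and 8.7.2.2.1, next sentence | all post-baseline, so 2, 4, 8, 12 | none |
| Table 14.2.6.1 title | 12 | none |
| Table 14.2.6.1 footnotes a, c, d | not stated | treatment p-value from a model with treatment-by-visit |
| SAP section 10 | list not corrected | none |

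Rows 1 and 2 cannot both hold unless Week 12 belongs in the list. No row names a Week 12 difference, odds ratio or contrast. The second page of the same table does not have this problem: its models take a single Week 12 value per patient, so the treatment p-value can only refer to Week 12.

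**2. Planning inputs (SAP section 9; allocation from 6.1.2).** Inflammatory means -16.7 and -12.2, so a difference of 4.5, SD 10.0. Non-inflammatory means -23.7 and -13.7, a difference of 10.0. IGA success 33.3% and 12.6%. Randomization 280:140, two-sided 0.05. The plan's inflammatory power reproduces: 274/137 gives 0.990 against the stated 99%.

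**3. Assumptions.** The documents give no effects at Weeks 2, 4 or 8, no visit-specific SDs and no between-visit correlations. I assumed these effects as fractions of the Week 12 effect (Weeks 2/4/8/12):

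- slow: 0.20/0.40/0.70/1
- middle: 0.25/0.50/0.80/1
- fast: 0.40/0.65/0.90/1

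I also assumed SD 10 at every visit, common correlation rho of 0.4 to 0.8, and an equal-weight average over visits.

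**4. Effect on the averaging reading.** Reported effect = planned effect x mean fraction.

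| Profile | Mean, Wk 2-8 | x 4.5 | x 10.0 | Mean, 4 visits | x 4.5 | x 10.0 |
|---|---|---|---|---|---|---|
| slow | 0.433 | 1.95 | 4.3 | 0.575 | 2.59 | 5.75 |
| middle | 0.517 | 2.33 | 5.2 | 0.638 | 2.87 | 6.4 |
| fast | 0.650 | 2.93 | 6.5 | 0.738 | 3.32 | 7.4 |

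For IGA, the planned odds ratio is (0.333/0.667)/(0.126/0.874) = 3.46, log 1.242.

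- Profile applied to the log odds ratio, exp(1.242 x mean fraction): 1.71, 1.90, 2.24 for Weeks 2 to 8, and 2.04, 2.21, 2.50 for four visits.
- Profile applied to both success rates, log odds ratios then averaged: 2.93, 3.00, 3.11 and 3.05, 3.11, 3.19.

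**5. Power, inflammatory lesions, 280/140.** SE = 10 x sqrt((1+(k-1)rho)/k) x sqrt(1/280+1/140), where k is the number of visits and the last factor is 0.1035. Power = Phi(effect/SE - 1.96).

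- Week 12 alone: SE 1.035, 4.5/1.035 = 4.35, power 0.99.
- Weeks 2 to 8, slow, rho 0.8: SE 0.964, 1.95/0.964 = 2.02, power 0.53.
- Weeks 2 to 8, fast, rho 0.4: SE 0.802, 2.925/0.802 = 3.65, power 0.95.
- Four visits, slow, rho 0.8: SE 0.954, 2.59/0.954 = 2.71, power 0.77.
- Four visits, fast, rho 0.4: SE 0.768, 3.32/0.768 = 4.32, power 0.99.

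**6. Boundary cases (two-sample t test, rho 0.3 to 0.7).**

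- Effect linear in time (0.75, 1.5, 3.0, 4.5 lesions): averages 1.75 and 2.44, power 0.47-0.64 and 0.76-0.93.
- Effect 3.0 at Weeks 2, 4 and 8 and zero at Week 12: the averaged test is significant with probability 0.90-0.98 (three visits) or 0.69-0.88 (four visits).
- Constant effect of 4.5 at every visit: power at least 0.99 on every reading.

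A visit-averaged p-value stands in for Week 12 only when the effect is roughly constant over visits.

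**The case against.** The strongest reply is that the documents largely settle the time point. All post-baseline visits include Week 12, and this SAP habitually sets the time point by title: the primary table (14.2.1.2) also shows one unlabelled mean per arm under a Week 12 title, while results at other visits carry a week label. On that view the list is an incomplete parenthesis carried over from the protocol. Also, a reference-coded IGA model with Week 12 as reference visit would give the Week 12 effect, so averaging is not the only default. Finally, the sizes come from assumed profiles, and a linear ramp falls below their range.

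Much of this stands. The intent probably is Week 12, and it would be wrong to say the plan excludes Week 12 data. The averaging reading is an inference, the magnitudes are illustrative, and the lesion-scale figures do not describe the ranked analysis in footnote c.

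It does not remove the defect. The primary table is safe because its model holds one value per patient; the repeated-measures model does not, so a title alone cannot identify the effect. A result that depends on software coding is not prespecified. The model was revised in the SAP without correcting the list or naming a contrast.

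**Conclusion.** The concern holds. As written, the visit list contradicts the next sentence and the table title, and the reported effect is undefined. The claim is that the text does not ensure a Week 12 test, not that Week 12 is certainly left out.

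On the averaging reading and the assumptions above, the lesion-count effects shrink to 43-65% of their planned size (Weeks 2 to 8) or 57.5-74% (four visits). The IGA odds ratio falls from 3.46 to 1.7-3.1 or 2.0-3.2. If the Week 12 contrast is what is reported, no number changes.

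The reach is limited to one of three sensitivity methods. The primary analysis, the gated secondary sequence, the model-based imputation and the tipping-point analyses are untouched. It should still be fixed before unblinding, because a contrast chosen afterwards would be post hoc and would weaken this analysis as evidence of robustness.

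**What to change.** Change the SAP only:

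1. In 8.1, 8.7.2.1.1 and 8.7.2.2.1, give the visit factor as Weeks 2, 4, 8 and 12.
2. On the first page of Table 14.2.6.1 and in footnotes a, c and d, state that the results are the Week 12 treatment contrast from the treatment-by-visit term: least-squares means, difference, confidence interval and p-value for lesion counts (p-value for the ranked version); odds ratio, confidence interval and p-value for IGA. The difference, odds ratio and interval are additions to the shell. Naming Week 12 is the essential part.
3. Record the change in section 10, noting that the protocol carries the same three-visit list.

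The cost is three wording edits, one section 10 entry, one table shell with its footnotes, and one contrast statement per model. No new data are needed. I see no need for a protocol amendment: the Preface says of the SAP and the protocol that the SAP "supersedes it in case of differences". The Preface does provide for considering an amendment when differences are major, such as a change to the primary-endpoint analysis. This correction leaves the primary analysis as it is, and the interaction term was itself recorded in SAP section 10 as a minor change.

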8.7.2.1.2 Model Based Multiple Imputation

The second sensitivity analysis will use the model based multiple imputation method to impute missing data for the absolute change in lesion counts at Week 12. The multiple imputation will involve 3 principal tasks:

1. Missing values will be filled in 5 times to generate 5 complete data sets. The imputation model used will be an ANCOVA with factors of treatment group and analysis center, and a covariate of Baseline lesion count (i.e., the imputation model will be the same as the analysis model).

Syntax:

```
proc mi data=datain out=dataout seed=&seed. nimpute=5 <options>;  
  class trtpn sitegr1;  
  var trtpn baseline sitegr1 week12;  
  monotone logistic (sitegr1=trtpn baseline);  
  monotone reg (week12=trtpn baseline sitegr1);  
run;
```

2. Each complete data set will be analyzed with an ANCOVA with factors of treatment group, and analysis center, and a covariate of Baseline lesion count. Appropriate modifications will be made should the analysis be based on a non-parametric method.
3. Results from these analyses will be combined into a single inference.

Two random seeds will be needed to impute the inflammatory and non-inflammatory lesion counts. The following random seed has been pre-specified by using a random number generator:

Inflammatory Lesion Count Seed= 1098696156

Non-inflammatory Lesion Count Seed= 1003722056

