8.7.2.2.2 Model Based Multiple Imputation

The second sensitivity analysis will use the model based multiple imputation method to impute missing data for the dichotomized IGA data. The multiple imputation will involve 3 principal tasks:

1. Missing values will be filled in 5 times to generate 5 complete data sets. The imputation model used logistic regression with factors of treatment group and analysis center (i.e., the imputation model will be the same as the analysis model).

Syntax:

```
proc mi data=datain out=dataout seed=&seed. nimpute=5 <options>;  
  class trtpn sitegr1 diiga;  
  var trtpn sitegr1 diiga;  
  monotone logistic (sitegr1=trtpn);  
  monotone logistic (diiga=trtpn sitegr1);  
run;
```

2. Each complete data set will be analyzed with a logistic regression a factors of treatment group and analysis center.
3. Results from these analyses will be combined into a single inference.

One random seed will be needed to impute IGA. The following random seed has been pre-specified by using a random number generator:

IGA Seed= 1857263794

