9. DETERMINATION OF SAMPLE SIZE

The following power calculations are based on the observed Week 12 results of the Phase 2 study, SGT-65-02. This study was a six-arm trial including S6G5T-3 and Vehicle Cream in the treatment of acne vulgaris. Estimates from the S6G5T-3 arm were used in the power assessments. The anticipated randomization ratio is 2:1 for S6G5T-3 and S6G5T-8 Vehicle Cream, respectively. The computations were performed with nQuery Advisor Version 7.0 using a two-sided test with a statistical significance value of 0.05.

A sample size of 274 in the S6G5T-3 and 137 in the Vehicle Cream group (total of 411) has 99% power to detect a statistically significant difference in inflammatory lesions. The estimated absolute change from Baseline in treatment means were -16.7 and -12.2 for S6G5T-3 and Vehicle Cream, respectively, with a common standard deviation of 10.0.

A sample size of 146 in the S6G5T-3 and 73 in the Vehicle Cream group (total of 219) has 99% power to detect a statistically significant difference in non-inflammatory lesions. The estimated absolute change from Baseline in treatment means were -23.7 and -13.7 for S6G5T-3 and Vehicle Cream, respectively, with a common standard deviation of 19.0.

A sample size of 231 in the S6G5T-3 and 116 in the Vehicle Cream has group (total of 346) has 99% power to detect a statistically significant difference the proportion of Patients who have at least a 2-grade reduction at Week 12 from Baseline in IGA and are Clear or Almost Clear. The estimated percentages with a 2-grade reduction at Week 12 from Baseline in the IGA and Clear or Almost Clear are 33.3% and 12.6% for S6G5T-3 and Vehicle Cream, respectively.

Therefore, a total of 420 Patients has adequate power to demonstrate statistical significance of S6GT5-3 over S6GT5-8 Vehicle Cream for the lesion count endpoints as well as dichotomized IGA.

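### The model-based imputation planned as the second sensitivity analysis is in effect a complete-case analysis and is not evidence of robustness to departures from missing at random

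*SAP*

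**What the plan says.** SAP 8.7.2.1.2 describes the second sensitivity analysis for lesion counts. Missing Week 12 values are drawn five times from an ANCOVA on treatment, center and baseline count, then analysed with that same ANCOVA. The text says that "the imputation model will be the same as the analysis model", and the code agrees: "monotone reg (week12=trtpn baseline sitegr1". Protocol 17.4.7.1 says the same.

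SAP 8.7.2.2.2 does the corresponding thing for dichotomized IGA, with a smaller model: "The imputation model used logistic regression with factors of treatment group and analysis center". Baseline IGA is not in it.

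The primary imputation (SAP 8.1.5.1 and 8.1.5.2) uses baseline and Weeks 2, 4, 8 and 12, separately in each arm. The SAP gives no specific purpose for the model-based imputation. It describes the tipping-point analyses (8.7.2.1.3 and 8.7.2.2.3) as the sensitivity analysis for how missing data are handled.

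**The concern.** When only the outcome is missing and it is drawn from the analysis model, the draws contain nothing that the completers' regression did not already contain. A patient who got worse through Week 8 and left is imputed as an average patient with the same arm, center and baseline. The primary imputation would use that patient's course.

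The analysis therefore stays within missing at random but conditions on less. It requires dropout to be unrelated to the course on treatment, given arm, center and, for lesion counts, baseline. Protocol 12.2 lists lack of efficacy, worsening and adverse events as reasons for withdrawal, so dropout related to course is foreseeable. Table 14.2.6.1 would report the result as a multiple imputation under a sensitivity heading, and a reader could take a complete-case estimate as independent support for the primary result.

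**Working it through.** **Inputs from SAP Section 9.** Test: "using a two-sided test with a statistical significance value of 0.05". Allocation: "The anticipated randomization ratio is 2:1". Inflammatory lesions: "treatment means were -16.7 and -12.2 for S6G5T-3 and Vehicle Cream, respectively", with a "common standard deviation of 10.0". The stated result is "total of 411) has 99% power to detect a statistically significant difference in inflammatory lesions".

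**Plan's own figure.** Vehicle n = (1 + 1/2) × (1.960 + 2.326)² × 10.0² / 4.5² = 1.5 × 18.37 × 100 / 20.25 = 136.1, so 137. Active is 2 × 137 = 274, total 411. This reproduces, so an effect of -4.5 with SD 10 is a fair basis for simulation. The plan gives no figure for the imputation analysis and no dropout rate.

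**Algebra, lesion counts.** Let b be the completers' least-squares estimate, with X_o and X_m the design rows of patients with observed and missing Week 12. On average over draws, the missing outcomes are filled with X_m b. Refitting to everyone gives

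(X_o'X_o + X_m'X_m)⁻¹ (X_o'y_o + X_m'X_m b) = (X_o'X_o + X_m'X_m)⁻¹ (X_o'X_o + X_m'X_m) b = b,

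because X_o'y_o = X_o'X_o b. The imputed patients leave the estimate at b whatever the dropout rate. Imputing the Week 12 count rather than the change makes no difference to the treatment coefficient, because baseline is a covariate. For logistic regression the argument is the same through the score equation, holding closely when there are many draws.

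**Simulation, lesion counts.** 280:140 patients, 300 trials per row. Assumed: 14 centers, adjacent-visit correlation 0.75, 10% or 20% missing at Week 12, Weeks 2, 4 and 8 observed for everyone. In the response-dependent rows, only active-arm dropout depends on response. Entries are mean estimate (mean SE).

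| Dropout | Full data | Complete-case | SAP model, 5 draws | SAP model, 100 draws | By arm, with Weeks 2/4/8 |
|---|---|---|---|---|---|
| Random, 10% | -4.45 | -4.45 (1.112) | -4.44 (1.119) | -4.44 (1.113) | -4.46 (1.084) |
| Random, 20% | -4.59 | -4.56 (1.183) | -4.59 (1.203) | -4.57 (1.183) | -4.55 (1.121) |
| On Week 8, 10% | -4.52 | -5.41 (1.084) | -5.40 (1.095) | -5.41 (1.085) | -4.52 (1.084) |
| On Week 8, 20% | -4.46 | -6.09 (1.132) | -6.09 (1.154) | -6.09 (1.134) | -4.49 (1.122) |
| On unseen Week 12, 10% | -4.43 | -5.59 (1.063) | -5.58 (1.071) | -5.59 (1.064) | -4.99 (1.052) |
| On unseen Week 12, 20% | -4.35 | -6.46 (1.109) | -6.44 (1.123) | -6.46 (1.110) | -5.34 (1.075) |

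The SD of the difference between the SAP model and complete-case is 0.14 to 0.25 lesions with 5 draws and 0.03 to 0.06 with 100. Monte Carlo noise should shrink by √(100/5) = 4.5. At 10% dropout on Week 8 the ratio is 0.148/0.033 = 4.5, so the difference is noise. Against full data, the SAP model overstates the effect by 5.40/4.52 - 1 = 19% at 10% dropout on Week 8, and by 6.09/4.46 - 1 = 37% at 20%.

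**Direction.** A second simulation (600 trials per scenario, true effect -4.5, 15-24% missing depending on Week 4/8 response) varied which arm lost its non-responders:

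- Vehicle only: SAP model -3.54, complete-case -3.55, visit-history imputation -4.56. Bias of the SAP model is (3.54 - 4.50)/4.50 = -21%.
- Active only: -5.23, -5.23 and -4.47. Bias (5.23 - 4.50)/4.50 = +16%.
- Both arms: -4.35, -4.36 and -4.51. Bias (4.35 - 4.50)/4.50 = -3%.

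**IGA.** Log odds ratios from 150 trials per dropout rate, with 8 centers assumed. At 10% missing: complete-case 1.434, SAP model 1.442 (5 draws) and 1.435 (50 draws), full data 1.302. At 20%: 1.513, 1.512, 1.514 and 1.248.

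**The case against.** The strongest objection is that nothing about robustness to informative dropout rests on this analysis. The lesion-count tipping point shifts only the imputed active-arm values, which is loss of benefit in active dropouts. The IGA tipping point covers every combination of imputed successes. In addition, SAP 8.1.5 keeps patients who left for a related AE or documented lack of effect in the per-protocol population with change from Baseline set to zero. That stands. A reader might infer that the plan never asks what happens if active-arm dropouts lose their benefit; the documents do not support that. What is missing is narrower. The zero-change rule covers two dropout reasons in the PP population. The lesion tipping point has no stated step, range or benchmark, and its table shell (14.2.7.1) shows only shifts and p-values. No planned ITT analysis gives an effect estimate under a named scenario.

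A reader might also infer that agreement with the primary teaches nothing. That goes too far. The second analysis adds center to the imputation model, pools the baseline slope and residual variance across arms, and imputes IGA as a binary outcome instead of rounding a normal draw. Agreement says something about those choices, and disagreement shows that the visit data matter. The changes are bundled, however, so a difference cannot be traced to one of them.

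Two limits are fair. If the skewness rule selects the ranked ANCOVA, SAP 8.7.2.1.2 promises only suitable modifications, and exact equivalence no longer follows. The bias sizes come from assumed dropout, and with non-responders leaving both arms the bias was only about 3%.

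**Conclusion.** The point holds in this form. For the parametric ANCOVA and the logistic model, the second sensitivity analysis is a complete-case analysis plus five-draw noise. That result is algebraic and needs no assumption about dropout, apart from many draws in the logistic case. The analysis needs a stronger assumption than the primary and does not probe departures from missing at random.

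Its bias is conditional. With dropout dependent on observed course it ranged from about -21% (poor responders leaving vehicle) to +37% (20% dropout, poor responders leaving active), and was close to zero under random dropout. It favours active only in the latter pattern, so the documents do not support a claim that it is biased towards the product in general. Nor is visit-history imputation a safeguard when dropout depends on unseen values: it gave -5.34 against a full-data -4.35. The primary analysis and its p-value are unaffected. This should be corrected because of how the result will be read.

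**What to change.** In SAP 8.7.2.1.2 and 8.7.2.2.2, before unblinding, supplement or replace the model-based imputation with a copy-reference multiple imputation on the ITT population:

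- Keep baseline and Weeks 2, 4 and 8 in the imputation model.
- Impute active-arm values after dropout from the vehicle-arm distribution.
- Analyse as in the primary and pool with PROC MIANALYZE.
- Record the change in SAP Section 10.

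If the present analysis is kept, state in both sections and in the footnote to Table 14.2.6.1 that it is equivalent to complete-case under the parametric and logistic models.

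The cost is SAP text, the Section 10 entry and a short program. Because the protocol specifies the model-based imputation, supplementing is simpler than replacing. The SAP supersedes the protocol where they differ (Section 2), but on replacement the sponsor should record whether it sees a need for an amendment. The sensitivity estimate will be somewhat less favourable to active. As a rough guide, if a fraction d of active patients took the vehicle mean and otherwise resembled those who stayed, an effect of 4.5 would become 4.5 × (1 - d): 4.05 at an assumed 10% and 3.60 at 20%.
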